6.4 Other Study Related Definitions

Analytical Study Week Assignments

Analytical windows will be used to assign parameters to study days/weeks. The algorithm is provided in [Appendix A](#).

Actual Treatment Group

A subject's actual treatment group is the randomized treatment group, unless the subject receives the same treatment throughout the study that is different to the randomized treatment group assignment, in which case the actual treatment group is the treatment received. For subjects randomized to omecamtiv mecarbil 37.5 mg BID and 50 mg BID, the actual treatment groups: 25 mg (Not up-titrated to 37.5 mg), 25 mg (Up-titrated to 37.5 mg) and 25 mg (Not up-titrated to 50 mg), 25 mg (Up-titrated to 50 mg) respectively, includes only those subjects who have a minimum IP exposure period of 25 days. Titration status groups may be used in select outputs and these four actual treatment groups should only be compared to each other. The omecamtiv mecarbil

Overall 37.5 mg BID, and Overall 50 mg BID actual treatment groups include all the subjects included in the omecamtiv mecarbil 37.5 mg BID, and 50 mg BID randomized treatment groups respectively.

Investigational Product (IP)

IP includes Omecamtiv Mecarbil 25 mg BID, 37.5 mg BID, and 50 mg BID and Placebo BID.

IP Dose Administered (mg)

From IP administration eCRF, number of tablets administered from each box is # dispensed - # lost or missing - # returned. If any of these numbers is missing, the sum of tablets reported on the IP administration eCRF for the same box will be used. IP dose administered is the sum of all the tablets' dose from all boxes dispensed.

IP Compliance (%)

Total IP dose administered divided by the total planned dose (223 tablets), multiplied by 100.

IP Exposure Period in Days

((Last IP administration date in the IP administration form – date of Study Day 1) + 1.

IP Exposure Period in Weeks

((Last IP administration date in the IP administration form – date of Study Day 1) + 1) / 7.

Study Exposure Period in Days

For each randomized subject, Study Exposure Period = (EOS Date – Randomization Date) + 1.

Study Exposure Period in Weeks

For each randomized subject, Study Exposure Period = ((EOS Date – Randomization Date) + 1) / 7.

Treatment-Emergent Adverse Event (TEAE)

Treatment Emergent adverse events are adverse events occurring between the first dose of IP and EOS. If an AE has an onset date after the date of first dose of IP, or the answer to the eCRF question “Did event start before first dose of investigational product?” is answered “no” then an event will be considered treatment emergent. The algorithm is provided in [Appendix B](#).

7. Analysis Subsets

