3.1 Study Design

This is a double-blind, randomized, placebo-controlled, multicenter, phase 2 study in Japanese HF subjects to evaluate 16 weeks of administration of oral MR omecamtiv mecarbil formulation at 3 dose levels (25 mg BID, 37.5 mg BID, and 50 mg BID), compared with placebo. Potential subjects will be screened to assess their eligibility to enter the study within 30 days prior to enrollment. Subjects are eligible for screening if they have chronic stable HF and reduced ejection fraction. Subjects may also be screened in the hospital setting once they have recovered and are considered clinically stable by the investigator. Subjects must be outpatients at the time of randomization.

Approximately 80 Japanese subjects with chronic stable HF with reduced ejection fraction will be randomized 1:1:1:1 to receive omecamtiv mecarbil either 25 mg BID dose (n=20), 37.5 mg BID dose (n=20), 50 mg BID dose (n=20) or placebo (n=20) on an outpatient basis. Subjects randomized to 37.5 mg BID target dose and 50 mg BID target dose will initiate administration at 25 mg BID and will be up-titrated to 37.5 mg BID or 50 mg BID respectively at the week 4 visit based on steady state concentration prior to investigational product (IP) administration ($C_{predose}$) result from week 2. Subjects who do not have a week 2 PK value in time for dose adjustment at the week 4 visit will be

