up-titrated at week 8 based on the steady state C_{predose} result from week 2, if available. Subjects will be up-titrated to 37.5 mg BID or 50 mg BID at the week 4 or week 8 visits in the titration groups only if the week 2 C_{predose} is < 200 ng/mL. Subjects with a week 2 $C_{\text{predose}} \geq 200$ ng/mL (or not available at week 8) will continue at 25 mg BID for the remainder of the study. Subjects randomized to placebo or to 25 mg BID will receive the assigned IP throughout the study. IP compliance will also be monitored. PK analysis and dose assignment will be blinded to the study team. To maintain blinding, all subjects will receive new IP supply at the week 4 and week 8 visits. The study includes transthoracic echocardiographic assessments (screening, week 8, and week 16). Enrollment of subjects with atrial fibrillation/flutter at the time of screening will be limited to approximately 20% of planned enrollment. Randomization will be stratified by presence or absence of atrial fibrillation/flutter via the interactive voice response system/interactive Web response system (IVRS/IWRS).

An independent DMC will perform regular formal unblinded review of the accumulating study data. An independent CEC will adjudicate deaths, all hospitalizations, and selected nonfatal cardiovascular (CV) events (including possible MI or ischemia). The end of study (EOS) visit will be performed 4 weeks after the last dose of IP (Week 20 +3 days).

Vital signs, physical examinations, ECGs, Adverse Event/Serious Adverse Event assessments, clinical laboratory evaluations (see Table 3 in protocol), and collection of concomitant medications will be performed at screening and at specified times per the Schedule of Assessments (see Table 2 in protocol). The overall study design is described by a study schema at the end of the protocol synopsis section. Detailed study procedures are provided in Protocol Section 7. The study endpoints are defined in [Section 4.1](#).

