10.1 General Principles

The final analysis will be conducted when all subjects have either completed all the scheduled study visits or have early terminated from the study. At that time, the database will be cleaned, processed and a snapshot will be taken; the study will also be unblinded. All endpoints will be analyzed based on this snapshot.

No formal hypothesis will be tested, and all statistical approaches are hypothesis-generating. Descriptive statistics will be presented for all endpoints.

Subject disposition, demographics, baseline characteristics and exposure to IP will be summarized.

Summary statistics for continuous variables will include number of subjects, mean, median, SD, or standard error, lower and upper quartiles, minimum, and maximum. For PK parameters, coefficient of variation (CV) will also be included. For categorical variables, frequency and percentage will be presented. Unless specified otherwise, all confidence intervals for estimates will be 2-sided with a significance level of 0.05.

Subjects will be analyzed based on their randomized or received treatment group assignment as described in [Section 7](#).

Missing data handling is specified in [Section 9.3](#).

For the secondary endpoint SET, sensitivity analyses using the CAS will be conducted to explore the robustness of selected results.

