10.8.5 Exposure to Investigational Product

Descriptive statistics will be produced to describe the exposure to investigational product by treatment group. Indicators of extent of IP exposure include total IP administration duration and dosing compliance.

Exposure definitions are provided in [Section 6.4](#).

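### SAP 6.4 divides a dose in mg by 223 tablets, so IP Compliance as written is not a percentage; the numerator should be the tablet count

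*SAP*

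**What the plan says.** SAP 6.4 builds compliance in two steps. The first definition is headed with the unit mg ("IP Dose Administered (mg"). It derives tablets taken per box as dispensed minus lost or missing minus returned, with the tablets reported on the administration eCRF as fallback. It then converts these to drug amount: "IP dose administered is the sum of all the tablets" multiplied out by dose over all boxes. The second definition is the compliance ratio, "Total IP dose administered divided by the total planned dose (223 tablets), multiplied by 100". The planned dose appears only as that one tablet count, with no mg equivalent by arm or titration path.

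SAP 6.4 also lists placebo as IP. In SAP 3.1 the two higher arms do not start at their target: "Subjects randomized to 37.5 mg BID target dose and 50 mg BID target dose will initiate administration at 25 mg BID". They move up at week 4 or week 8. Those whose week 2 trough is 200 ng/mL or more ("or not available at week 8) will continue at 25 mg BID for the remainder of the study") never do.

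The figure is reported. SAP 10.8.5, which summarises exposure by treatment group, states: "Indicators of extent of IP exposure include total IP administration duration and dosing compliance". SAP 10.1 adds that continuous summaries include "lower and upper quartiles, minimum, and maximum". The companion measure, the IP Exposure Period in SAP 6.4, runs from Day 1 to the "Last IP administration date in the IP administration form".

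**The concern.** A percentage needs the same unit above and below the line, and this one does not have it. No single factor repairs the mismatch: placebo tablets carry no mg of drug, and a subject in the 37.5 or 50 mg arm may take two strengths in sequence or stay at 25 mg. A programmer following the text literally gets an impossible number. One who sees the problem has to choose a repair that the SAP does not name.

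At stake is one of the two exposure indicators that SAP 10.8.5 names, in a study with safety and tolerability among its primary objectives. A secondary matter is the fixed denominator. Even with the numerator corrected, 223 is applied to everyone, whatever day the last dose falls on and whether or not the subject stopped early, so the label compliance says more than the number measures.

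**Working it through.** **Inputs.** Dosing is twice daily from the morning of Day 1 to the morning of the week 16 visit (Protocol 6.2.1.1). Week 16 is Day 112, with a window of 3 days either side (Protocol 7.1, Table 2). Week 4 is Day 28. One tablet per dose is inferred: Protocol 2.3 mentions a separate 37.5 mg strength, but the IP manual is not among the documents. Up-titration is placed at the Day 28 morning dose.

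**Reproducing 223.** Tablets to a last morning dose on day D = 2 x (D - 1) + 1. For D = 112: 2 x 111 + 1 = 223. This matches the SAP exactly.

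**Literal rule, mg / 223 x 100, no dose missed, last dose Day 112.** Before Day 28 there are 27 x 2 = 54 tablets at 25 mg, leaving 223 - 54 = 169 at target.

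| Arm | mg administered | mg / 223 x 100 |
|---|---|---|
| Placebo | 0, or not defined | 0, or no value |
| 25 mg | 223 x 25 = 5575 | 2500% |
| 37.5 mg, up-titrated Day 28 | 54 x 25 + 169 x 37.5 = 7687.5 | 3447% |
| 50 mg, up-titrated Day 28 | 54 x 25 + 169 x 50 = 9800 | 4395% |
| 37.5 or 50 mg, never up-titrated | 223 x 25 = 5575 | 2500% |

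**Tablets / 223 x 100.** Every subject in the table scores 223/223 = 100%, including placebo and those kept at 25 mg. Titration path drops out.

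**What the fixed denominator does.**
- Full adherence at the window edges: Day 109 gives 2 x 108 + 1 = 217, and 217/223 = 97.3%. Day 115 gives 2 x 114 + 1 = 229, and 229/223 = 102.7%.
- Adherent until a permanent stop on the morning of Day 28 (assumed): 2 x 27 + 1 = 55, and 55/223 = 24.7%.
- Adherent until a permanent stop on the morning of Day 84 (assumed): 2 x 83 + 1 = 167, and 167/223 = 74.9%, with an exposure period of 84 days.
- A 28-day hold resumed to Day 112 (assumed): 223 - 56 = 167, again 74.9%. The exposure period is 112 days, although only 112 - 28 = 84 days were dosed.

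The last two subjects have the same percentage and the same number of dosed days. Their exposure periods differ, because the IP Exposure Period counts the withheld days before a resumed dose.

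**The case against.** The strongest reply is that no competent programmer would be misled. The tablet count is derived one definition earlier, the denominator is stated in tablets, and 223 fits the dosing schedule exactly. A result of 2500% would not survive the output verification in SAP 9.7. All of this stands. It shows that the intent can be recovered and that the damage is small. It does not make the written rule right.

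Three stronger inferences are tempting, and the documents do not support them.

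- *That compliance cannot be computed.* This is true only of the literal wording. Tablets over 223 works in every arm.
- *That protocol-directed titration will look like non-compliance that worsens with dose.* Dividing mg by 223 times the target dose would do this: 7687.5/8362.5 = 91.9% at 37.5 mg and 9800/11150 = 87.9% at 50 mg for adherent subjects up-titrated on Day 28. But the SAP contains no such denominator.
- *That the fixed denominator is itself an error, because it brands a subject stopped for safety as non-compliant.* The SAP sets no compliance threshold and classifies nobody. A planned-course denominator is defensible. Counting planned tablets only to each subject's own last dose would lift the adherent Day 28 stopper from 24.7% to 55/55 = 100% and leave the resumed 28-day hold at 167/223 = 74.9%. That is a trade-off. Permanent stops already appear in the discontinuation reasons (SAP 10.2), in AEs leading to IP withdrawal (SAP 10.8.1) and in exposure duration (SAP 10.8.5).

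**Conclusion.** The point holds as a unit error in a stated definition, of minor severity. Read literally, the rule gives about 2500% to 4395% for fully adherent subjects on active drug and 0 or nothing for placebo. Read as evidently intended, it gives 100% in every arm for a last dose on Day 112, and 97.3% to 102.7% across the week 16 window.

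The effect stops at one descriptive exposure summary. The PK, full, safety and completer sets in SAP 7 are defined by doses received, evaluable concentrations or completion of IP. The titration-status groups in SAP 6.4 use days of exposure. The PK analysis in SAP 10.5 uses actual doses. None of them uses the compliance figure, so no trough, AUC or SET result moves.

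The figures assume one tablet per dose and a switch at the Day 28 morning dose. The hold length and stop days are illustrations; the documents give no rates for either.

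**What to change.** 1. In SAP 6.4, define IP Compliance (%) as 100 x number of tablets administered / 223 in all arms, including placebo. Tablets administered is dispensed minus lost or missing minus returned, summed over boxes, with the existing eCRF fallback. Keep the mg total as a separate quantity.
2. Label the result *percent of planned 16-week tablets*, and state that 223 applies to every subject, including early stoppers and those whose week 16 visit falls off Day 112.
3. Optional: in SAP 10.8.5, report days dosed (calendar days with at least one recorded dose) beside the IP Exposure Period. This makes a resumed hold visible, such as 84 of 112 days in the example above, but does not give the reason for it.

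Items 1 and 2 are text edits that use a count the SAP already derives, and they need no new data. Item 3 adds one derived variable from the dose dates and times that sites transcribe from the diary (Protocol 7.2.5).

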3. EXPERIMENTAL PLAN

3.1 Study Design

This is a double-blind, randomized, placebo-controlled, multicenter, phase 2 study in Japanese HF subjects to evaluate 16 weeks of administration of oral MR omecamtiv mecarbil formulation at 3 dose levels (25 mg BID, 37.5 mg BID, and 50 mg BID), compared with placebo. Potential subjects will be screened to assess their eligibility to enter the study within 30 days prior to enrollment. Subjects are eligible for screening if they have chronic stable HF and reduced ejection fraction. Subjects may also be screened in the hospital setting once they have recovered and are considered clinically stable by the investigator. Subjects must be outpatients at the time of randomization.

Approximately 80 Japanese subjects with chronic stable HF with reduced ejection fraction will be randomized 1:1:1:1 to receive omecamtiv mecarbil either 25 mg BID dose (n=20), 37.5 mg BID dose (n=20), 50 mg BID dose (n=20) or placebo (n=20) on an outpatient basis. Subjects randomized to 37.5 mg BID target dose and 50 mg BID target dose will initiate administration at 25 mg BID and will be up-titrated to 37.5 mg BID or

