7. STUDY PROCEDURES

7.1 Schedule of Assessments

Table 2. Schedule of Assessments

Timepoint - Day/Week/Month (window)*	Screen	D1	D7	W2 D15 (-3)	W4 D28 (+3)	D34 (+3)	W8 D56 (±3)	D62 (+3)	W12 D84 (±3)	W16 D112 (±3)	W20 ^a D140(+3) EOS
General Procedures											
Informed consent	X										
Medical history and demographics	X										
Vital Signs (HR, BP)	X	X ^c		X	X		X ^j		X	X ^k	X
AEs/SAEs/PEPs ^b	X	X		X	X		X		X	X	X
AEs/SAEs and IP compliance verification by phone or other contact			X			X		X			
Concomitant therapy	X	X		X	X		X		X	X	X
Physical examination	X										X
Body height		X									
Body weight		X		X			X		X	X	X
ECG	X	X ^c		X	X		X ^d		X	X ^d	X
Echocardiogram	X						X ^j			X ^k	
Central Laboratory											
PK samples ^e		X ^c		X ^c	X ^c		X ^j		X ^c	X ^k	
Chemistry (including eGFR at screening)	X			X			X		X	X	X
Hematology	X			X			X		X	X	X
Urinalysis		X					X				X
Troponin I, CK-MB ^e		X ^c		X	X		X		X	X	X
NT-proBNP		X ^c			X		X			X	
Samples for Development Therapeutic Monitoring Assay					X				X		
Serum pregnancy, FSH/LH or estradiol ^f	X										X
Digoxin sample (in subjects receiving digoxin)		X		X							
Investigational Product^g											
IP dispensation and/or administration at site		X		X	X		X		X	X ^h	
IP diary dispensation or collection ⁱ		X								X	
IP reconciliation (tablet count)				X	X		X		X	X	

Footnotes displayed on the next page of the Table

AE = adverse event; BP = blood pressure; CK-MB = creatine kinase-MB; ECG = electrocardiogram; eGFR = estimated glomerular filtration rate; EOS = end of study; HR = heart rate; IP = investigational product; NT-proBNP = N-terminal pro-B-type natriuretic peptide; NYHA = New York Heart Association; PEP = potential endpoint; PK = pharmacokinetic; SAE = serious adverse event.

Please note: vital signs, ECGs, and laboratory samples can be collected at any time during the study visit, unless otherwise specified below.

Visit Windows: For week 2 visit, the visit date could be 3 days prior to the scheduled date of W2; for week 4 visit, the visit date could be 3 days after the scheduled date of W4; for weeks 8, 12, and 16, the visit dates could be 3 days prior to or after the scheduled date of W8, W12, and W16, respectively; for week 20 visit (EOS), the visit date could be up to 3 days after the scheduled date of W20. The Day 34 and 62 telephone calls could be 3 days after the scheduled date of contact.

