^a If early discontinuation, week 20 (EOS) assessments should be performed as close as possible to time of discontinuation

^b Serious adverse events are collected from signing the informed consent until 30 days after the last dose of IP or EOS, whichever is later, adverse events and PEPs from randomization until EOS, recording of PEPs and hospitalization only during visits to the study site (day 1, weeks 2, 4, 8, 12, 16, 20 [EOS]); if subject is not seen at the study site, AEs/SAEs/PEPs can be collected by phone

^c Predose in the morning, at study site

^d Performed as close as possible after the collection of PK sample at 2 hours \pm 30 minutes following IP administration.

^e If cardiac troponin is measured locally to evaluate suspected myocardial ischemia or infarction, send samples for troponin I/CK-MB, and PK (up to 5 days after last dose of IP) to the central laboratory

^f Serum pregnancy testing in females of childbearing potential, FSH/LH or estradiol at screening only, and only if applicable per exclusion criteria.

^g IP is taken twice daily except on the last day of administration (week 16 visit). Subjects randomized to 37.5 mg BID target dose and 50 mg BID target dose will initiate administration at 25 mg BID. Subjects will be up-titrated to 37.5 mg BID or 50 mg BID target dose at the week 4 visit based on steady state $C_{predose}$ result from week 2. Subjects who do not have a week 2 PK value in time for dose adjustment at the week 4 visit, will be up-titrated at week 8 based on steady state $C_{predose}$ result from week 2, if available. Subjects will be up-titrated at the week 4 or week 8 visits only if the week 2 $C_{predose}$ is < 200 ng/mL. Otherwise, they will continue at 25 mg BID.

^h Details of IP dispensation and reconciliation are described in the IPIM; dispensation and reconciliation timepoints may differ from the timepoints shown above; IP not dispensed at week 16 visit.

ⁱ Paper Diary will be dispensed at Day 1 and will be collected at week 16. Subjects will be instructed to enter each administration of IP from Day 1 to week 16 or early termination. The date and time of administration will be noted.

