10.8.1 Adverse Events

The Medical Dictionary for Regulatory Activities (MedDRA), using the current version at the time of final database lock, will be used to code all adverse events (AEs) to a system organ class and a preferred term. All adverse event tables will be summarized by actual treatment group. Treatment-emergent adverse events are events with an onset after the administration of the first dose of investigational product through the end of study as defined in [Section 6.3](#).

The subject incidence of AEs will be summarized for all treatment-emergent AEs (TEAEs), serious AEs, AEs leading to withdrawal of investigational product, fatal AEs, and AEs of interest (EOI).

Subject incidence of all treatment-emergent AEs, serious AEs, AEs leading to withdrawal of investigational product, and fatal AEs will be tabulated by system organ class and preferred term in descending order of frequency.

Summaries of treatment-emergent and serious AEs by preferred term in any treatment arm will be provided in descending order of frequency.

Subject incidence of EOIs (structured MedDRA queries and/or customized queries) will be summarized according to the EOI search strategy categories.

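### Adverse event tables pool the 25 mg start, the target-dose period and the off-drug follow-up, so none isolates tolerability at 37.5 or 50 mg, and the 25-day titration-group rule precedes the day 28 visit

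*SAP*

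**What the plan says.** SAP 6.4 sets the counting window: "Treatment Emergent adverse events are adverse events occurring between the first dose of IP and EOS". Neither that section nor SAP Appendix B splits events by the dose taken at onset or sets a cut-off after the last dose. SAP 10.8.1 adds: "All adverse event tables will be summarized by actual treatment group".

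Under the SAP 6.4 definition of actual treatment group, the 37.5 and 50 mg arms each appear in two forms:

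- An overall group. The "Overall 37.5 mg BID, and Overall 50 mg BID actual treatment groups include all the subjects included in" the corresponding randomised arms, with no exposure minimum.
- Titration-status groups, up-titrated or not up-titrated, four in all. Membership "includes only those subjects who have a minimum IP exposure period of 25 days". On their use the SAP says: "Titration status groups may be used in select outputs and these four actual treatment groups should only be compared to each other".

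The dosing calendar comes from the protocol. Section 3.1: "Subjects randomized to 37.5 mg BID target dose and 50 mg BID target dose will initiate administration at 25 mg BID". The week 4 visit is day 28, and under Table 2 "for week 4 visit, the visit date could be 3 days after the scheduled date of W4"; no earlier date is allowed. A subject whose week 2 concentration arrives too late "will be up-titrated at week 8 based on steady state" concentration. Dosing ends on the morning of the week 16 visit, day 112 (Protocol 6.2.1.1), and the end-of-study visit follows 4 weeks later, day 140.

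**The concern.** Safety and tolerability is one of the two primary objectives, and the design sets three dose levels against placebo. Table 1 of the protocol simulates a mean steady-state AUC in Japanese subjects of 2759 ng*hr/mL at 25 mg BID and 6143 at 50 mg BID, a ratio of 6143/2759 = 2.2. If the higher dose causes adverse events, they should begin at the step from 25 mg. A table that starts at the first 25 mg tablet and ends four weeks after the last tablet mixes those events with background events from periods when the subject was not on the higher dose. Dose groups then look more alike than they are.

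The 25-day rule raises a second, smaller question. If it is meant to limit the titration-status groups to subjects who reached the titration decision, it is set too early.

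**Working it through.** **1. Check the calendar against the plan's own figure.** SAP 6.4 gives a total planned dose of 223 tablets. Two tablets on each of days 1 to 111 plus one on the morning of day 112 is 2 × 111 + 1 = 223. This matches, so on-drug time is days 1 to 112.

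**2. Divide the 140-day window.** Days at 25 mg = titration day − 1. Days at target dose = last dose day − titration day + 1. Days off drug = end-of-study day − last dose day. Target dosing is taken to start on the titration visit day.

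| | 25 mg | Target dose | Off drug |
|---|---|---|---|
| Titrated week 4 (day 28) | 27 (19.3%) | 85 (60.7%) | 28 (20.0%) |
| Titrated week 8 (day 56) | 55 (39.3%) | 57 (40.7%) | 28 (20.0%) |

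If target dosing starts the next day, the target periods are 84 and 56 days (60% and 40%). Over the extremes of the visit windows, the target-dose share runs from 79/143 = 55% to 88/140 = 63% for week 4 titration, and from 51/143 = 36% to 63/140 = 45% for week 8.

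**3. Drug remaining after the last dose.** Protocol 2.2.2.1 reports a mean half-life of 17.1 to 23.2 hours (IV dosing, healthy men). After 5 days (120 h) the fraction left is 2^(−120/17.1) = 0.8% to 2^(−120/23.2) = 2.8%. On that half-life, about 23 of the 28 follow-up days are essentially drug-free.

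**4. Illustrate the dilution.** The documents give no adverse event rate for this population, so this step is assumed: a constant background hazard λ, doubled only on target-dose days, and placebo incidence p over 140 days. Then λ = −ln(1 − p)/140 and I(x) = 1 − exp(−λx), where x is hazard-weighted days. Taking 84 target-dose days and p = 30%:

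- Whole window: I(56 + 2 × 84) = I(224) = 43.5%, against I(140) = 30.0%. Ratio 1.45, difference 13.5 points.
- Target-dose days only: I(168) = 34.8%, against I(84) = 19.3%. Ratio 1.81, difference 15.5 points.
- Week 8 titration, whole window: I(84 + 2 × 56) = I(196) = 39.3%. Ratio 1.31.

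The same formulas for week 4 titration over a range of p:

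| p | Whole-window ratio (difference) | Target-dose ratio (difference) |
|---|---|---|
| 20% | 1.50 (10.0 points) | 1.87 (11.0 points) |
| 30% | 1.45 (13.5 points) | 1.81 (15.5 points) |
| 60% | 1.28 (16.9 points) | 1.58 (24.4 points) |

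**5. The 25-day rule.** SAP 6.4 defines the exposure period as last dose date minus Study Day 1 date, plus 1, so 25 days means a last dose on day 25. The earliest in-window titration is day 28. Every subject titrated within window therefore has at least 28 days of exposure, and the rule excludes none of them. Subjects who stop on day 25, 26 or 27 pass the rule without having reached the visit. They fall into the not up-titrated groups, beside subjects held at 25 mg because the week 2 concentration was at least 200 ng/mL or was still unavailable at week 8.

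**The case against.** The case for leaving the plan alone has several sound parts.

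- The study is descriptive. Counting from first dose to end of study matches the protocol's collection period and applies equally to every arm. What was randomised is a titration regimen, and a table by randomised arm describes it properly.
- A reader might infer that the SAP counts 25 mg and off-drug days as time at the target dose. It does not. The tables are subject incidences without person-time, and the titration-group labels show the 25 mg start.
- A reader might also infer that the 25-day rule strips early intolerant subjects out of the up-titrated groups or out of safety reporting. Neither follows. Up-titration itself requires remaining on drug to day 28, so the rule removes nobody from those groups. The overall groups keep every dosed subject in the arm, and events leading to withdrawal of study drug are tabulated separately.
- The illustration looks more striking as a ratio than as a difference. At p = 30% and 20 subjects per arm, 13.5 against 15.5 points is 2.7 against 3.1 excess subjects.
- The misfiling under the 25-day rule concerns a three-day stopping window in about 40 subjects.
- The off-drug month applies to completers. After early discontinuation, Table 2 places the end-of-study assessments close to stopping.

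All of this stands, and it limits the point. It does not supply a summary at the target dose. Nor does the optional status of the titration-group outputs settle the matter. The protocol synopsis commits to summarising safety endpoints by titration status as well as by randomised group, and SAP 7.3 treats subjects held at 25 mg as separate schemas because of their drug levels. The four titration-status groups may be compared only with each other, so they have no placebo reference.

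**Conclusion.** The point holds as a gap in the adverse event analysis, not as an error in the overall table. No planned output isolates events with onset at 37.5 or 50 mg. For completers in those arms, about 39% of the window is not at target dose after week 4 titration, and about 59% after week 8 titration. The stronger reading, that the tables say nothing about tolerability at these doses, is not supported, since 84 or 85 of 140 days are at target dose after week 4 titration.

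The day counts rest on nominal visit days. The size of the dilution rests on assumed incidences and an assumed doubling of hazard confined to target-dose days; an effect already present at 25 mg would be diluted less.

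The mismatch between 25 days and the day 28 visit is real but small. It affects only the not up-titrated groups. One conditioning effect remains in the up-titrated groups whatever the rule: early events in subjects who stayed on drug are counted, while subjects who stopped permanently before day 28 cannot appear. This is a further reason not to count pre-titration events in those tables.

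**What to change.** Keep the planned overall table. In SAP 6.4 and 10.8.1, add treatment-emergent incidence with person-time by onset period, for every arm including placebo. Anchor the periods on the supply visits that all arms share:

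1. First dose to the day before the week 4 supply, with the three active arms (about 60 subjects, all on 25 mg) pooled against placebo.
2. First dose of the week 4 supply to last dose + 5 days, by randomised arm and titration status.
3. After that to end of study.

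For subjects titrated at week 8, attribute events to the dose taken at onset. If any late titrations occur, split period 2 at week 8 in all arms so that each part has a placebo counterpart. In the titration-status tables, count period 2 events only.

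Replace the 25-day rule with status by what happened: up-titrated (took at least one target dose); not up-titrated because of the concentration rule or an unavailable result; or stopped study drug before the titration decision, shown separately. Merely requiring a dose from the week 4 supply would not be enough, because a subject who stops while waiting for week 8 titration would still be filed as not up-titrated.

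The 5-day limit follows the one the protocol already uses after the last dose for PK sampling, contraception and pregnancy reporting. The supporting half-life comes from IV dosing in healthy men, so the SAP should state the limit as an assumption for the oral tablet in heart failure.

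The cost is SAP wording and a few tables. Event onset and dosing dates are already collected, and no procedure or dosing rule changes. The downside is fewer events in each period table. While editing, correct the cross-reference in SAP 10.8.1, which points to Section 6.3 for a definition that stands in 6.4.
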